### **Time to best response (TTBR)**

TTBR is defined as the time from randomization to the date of first occurrence of IRC determined best overall response (PR or better) that is subsequently confirmed. In the absence of response patients will be censored at the earliest of the date of the last valid disease assessment before

disease progression or death, the date of the last valid disease assessment before initiation of a further anti-myeloma treatment (if any) or the analysis cut-off date, whichever comes first.

### **Minimal residual disease (MRD)**

MRD will be assessed by next-generation sequencing in bone marrow samples from patients who achieve CR, to determine the depth of response at the molecular level.

#### *2.1.3.2.3 Other exploratory efficacy endpoints*

### **PFS2**

PFS2 is defined as time from the date of randomization to the date of first documentation of PD (as reported by the investigator) after initiation of further anti-myeloma treatment or death from any cause, whichever happens first. For patients alive without a progression after initiation of further anti-myeloma treatment before the analysis cut-off date, PFS2 will be censored at the date of the last follow-up visit not showing disease progression after initiation of further anti-myeloma treatment or the analysis cut-off date, whichever comes first. Additional details regarding the definition of PFS2 and handling of events and censoring are given in [Appendix H](#).

### **ORR on further therapy**

ORR on further anti-myeloma treatments will be based on BOR as reported by the investigator.

### **PFS on first line of further therapy**

PFS on first line of further therapy is defined as time from the start date of first line of further therapy to the date of first documentation of PD (as reported by the investigator) after initiation of first line of further therapy or death from any cause, whichever happens first. For patients alive without a progression after initiation of further therapy before the analysis cut-off or the start date of next line of further treatment, PFS on further therapy will be censored at the earliest of the date of the start of next line of further treatment (if any), the date of the last follow-up visit not showing disease progression or the analysis cut-off date, whichever comes first.

If the first line of further therapy includes daratumumab then the start date of first line of further therapy will be defined as the start date of daratumumab.

## **2.1.4 Safety endpoints**

The safety analysis will be based on the reported adverse events (AEs) and other safety information, such as clinical laboratory data, vital signs, weight and Eastern Cooperative Oncology Group (ECOG) performance status (PS).

### ***Observation period***

The observation period starts from the time when the patient gives informed consent and is divided into 3 periods:

- The **pre-treatment** period is defined as the time from the signed informed consent date up to the first dose of study treatments.
- The **treatment** period is defined as the time from the first dose of study treatments administration to the last dose of study treatments + 30 days.
- The **post treatment** period is defined as the period of time starting the day after the end of the treatment period up to the end of the study (as defined in the protocol).

#### ***2.1.4.1 Adverse events variables***

AEs (including serious adverse events [SAEs] and AEs of special interest [AESI]) will be collected from the time of signed informed consent until the end of study.

##### **Adverse event observation period**

- Pre-treatment adverse events are defined as any adverse event reported during the pre-treatment period.
- Treatment-emergent adverse events (TEAEs) are adverse events that developed or worsened or became serious during the treatment period.
- Post-treatment adverse events are adverse events that developed or worsened or became serious during the post-treatment period.

All AEs (including SAEs and AESI) will be graded according to National cancer institute common terminology for adverse events (NCI-CTCAE) v4.03 and coded to a lower-level term (LLT), preferred term (PT), high-level term (HLT), high-level group term (HLGT) and associated primary system organ class (SOC) using the version of Medical Dictionary for Regulatory Activities (MedDRA) currently in effect at Sanofi at the time of database lock.

##### **Adverse events of special interest**

AESI include the following terms:

- Acute infusion reactions (IRs) of Grade 3 or 4.
- Pregnancy of female patient entered in a study as well as pregnancy occurring in a female partner of a male entered in a study with IMP.
- Symptomatic overdose (serious or non-serious) with study treatment (isatuximab, pomalidomide or dexamethasone).
- Second Primary Malignancy.

### **Infusion reactions**

IRs are commonly observed with monoclonal antibodies and typically occur within 24 hours from the start of each isatuximab infusion.

Whenever possible, a diagnosis of the IR (eg, Cytokine release syndrome, infusion related reaction, anaphylactic reaction, hypersensitivity) will be reported by the investigator in a specific AE page instead of individual symptoms.

In addition, symptoms of the IRs will be reported on a separate eCRF form.

IRs will be analyzed using the Investigator reported term collected in the specific AE forms.

Another analysis will be based on any TEAEs (both regardless of relationship and related TEAEs) occurring within 24 hours from the start of any isatuximab infusion (ie, TEAEs with onset on the same calendar day of the isatuximab infusion or on the following day).

A similar analysis including TEAEs occurring within 24 hours in the “Hypersensitivity and CRS” CMQ will also be performed.

All TEAEs (not only limited to those occurring within 24h of any isatuximab administration) from the above listed CMQ will also be analyzed in both arms.

### **Respiratory AEs**

Analysis of selected respiratory TEAEs will focus particularly on the following groupings:

- Lower Respiratory adverse events, selected using CMQ ‘Lower respiratory events’.
- Respiratory infections, selected using CMQ ‘Respiratory infections’.

Late respiratory adverse events (ie, occurring, worsening or becoming serious more than 30 days after last dose) will be analyzed as part of the post-TEAEs analysis.

### **Neutropenia and neutropenic complications**

Neutropenia, febrile neutropenia and neutropenic infections will be analyzed using the following data source:

- Neutropenia based on laboratory results.
- Febrile neutropenia selected using CMQ ‘Febrile neutropenia’
- Neutropenic infections: defined as NCI-CTCAE Grade  $\geq 2$  infections from SOC ‘Infections and Infestations’ (selected using CMQ ‘GLB\_SOC infections and infestations’) concomitant with NCI-CTCAE Grade 3-4 neutropenia from laboratory results. Infection and Grade 3-4 neutropenia will be considered as concomitant if one of the following condition is met:
  - neutrophils count value measured the day of the start of the AE infection,

- the last neutrophils count value measured before the start date of the AE infection is within 7 days before the start of the AE infection,
- the first neutrophils count value measured after the start date of the AE infection is within 2 days after the start of the AE infection.

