- m* **Hematology:** To be done at screening and to be repeated within 24 hours prior to study treatment administration on Cycle 1 Day 1 (prior to premedication in IPd arm and prior to pomalidomide administration in Pd arm on Day 1), within 24 hours prior to study treatment administration on Day 8, Day 15 and Day 22 of Cycle 1, within 24 hours prior to study treatment administration on Day 1 and Day 15 at Cycle 2 and Cycle 3, and then within 24 hours prior to study treatment administration on Day 1 of every subsequent cycle, at the EOT visit, and as clinically indicated. Hematology includes: hemoglobin, hematocrit, RBC, WBC with differential, ANC and platelet count. If G4 neutropenia, assess ANC every 2-3 days until ANC $\geq 0.5 \times 10^9/L$ and at least weekly thereafter until ANC $\geq 1.0 \times 10^9/L$. Hematological abnormalities will be recorded as AEs only if they are serious or lead to study treatment modification or discontinuation.
- n* **Antibody screening test (IPd arm only):** Blood typing and complete blood phenotyping (C,c; E,e; Kell, Kidd; Duffy; S,s is recommended, if not available follow site's standard) if not already done, and antibody screening (Indirect Coombs Test, Indirect Antiglobulin Test [IAT]) to be obtained after randomization prior to Cycle 1 Day 1 study treatment administration. IAT to be repeated at Cycle 2 Day 1; if the test is not performed at this visit, it can be done at the next blood sampling. Results of IAT will be recorded in eCRF, including those performed prior to any transfusion during study treatment. Transfusions are to be recorded in the eCRF. Blood type card will be kept by the patient with the study card and the blood bank needs to be informed that the patient is receiving a treatment with an anti-CD38 and a potential interference with the Indirect Coombs test is possible.
- o* **Coagulation:** To be done at screening and then as clinically indicated. Coagulation includes: prothrombin time, international normalized ratio, and activated partial thromboplastin time.
- p* **Urinalysis:** To be done at screening and then as clinically indicated. Quantitative urinalysis at baseline, and qualitative (dipstick) after start of study treatment. This includes for quantitative: red blood cells, protein, glucose, pH, ketones, bilirubin, leucocytes; and for qualitative: blood, protein, glucose, pH, ketones, bilirubin, leucocytes.

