8.2.3 Dose modifications

8.2.3.1 General rules

Dose modifications are permitted according to the guidelines described in this section.

Dose reduction for pomalidomide and low-dose dexamethasone and/or cycle delay (ie, delay of all study treatments) are permitted in case of toxicity. Patient may have dose omitted (isatuximab and/or pomalidomide and/or dexamethasone) within a cycle if toxicity occurs and the patient does not recover by the day of planned infusion/administration. If a patient experiences several toxicities and there are conflicting recommendations, the most conservative dose adjustment recommended (dose reduction/omission/delay appropriate to the most severe toxicity) should be followed. Once a dose of pomalidomide or dexamethasone has been decreased, intra-patient re-escalation back to the previous dose level is not permitted.

Administration of the study treatment (isatuximab and/or pomalidomide and/or dexamethasone) will be discontinued in the event of an AE that persists despite appropriate dose modifications or any other AE that, in the opinion of the Investigator, warrants discontinuation.

All changes to study treatment administration must be recorded in the eCRF.

Patients will receive the next cycle of study treatment after recovery of the toxicity as described below.

A new cycle of study treatment may begin on the scheduled Day 1 of a subsequent cycle if the following criteria are met.

- ANC $\geq 1000/\text{mm}^3$.
- Platelet count $\geq 50\ 000/\text{mm}^3$. For patients with plasma cells $\geq 50\%$ of bone marrow nucleated cells at baseline, to initiate Cycle 2, platelet counts should be $\geq 30\ 000/\text{mm}^3$ regardless response status at end of Cycle 1. During Cycles 2-4, platelet counts should be $\geq 30\ 000/\text{mm}^3$, if last response is not better than SD, but if last response is PR or better during Cycles 2-4, D1 next cycle can be administered only if platelet counts $\geq 50\ 000/\text{mm}^3$. For D1 administration beyond Cycle 4, platelet counts should be $\geq 50\ 000/\text{mm}^3$.

Any other pomalidomide, dexamethasone or isatuximab related AE that may have occurred in the previous cycle has recovered to \leq G1 or baseline severity (or according to the dose modifications shown in [Section 8.2.3.3](#) and [Section 8.2.3.4](#)).

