### **Thrombocytopenia and hemorrhages**

- Thrombocytopenia will be analyzed based on laboratory results
- Hemorrhages will be selected using the TEAEs from the CMQ ‘Haemorrhage terms (excl laboratory terms)’.
- Moreover, severe thrombocytopenia (ie, Grade 4) with concomitant hemorrhage will be displayed if relevant (ie, in case of imbalance between treatment arms). The first hemorrhages event occurring within 8 days after any occurrence of the thrombocytopenia (Lab) will be used for this analysis.

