### ***Thrombocytopenia and hemorrhages***

The number (%) of patients will be provided for:

- On-treatment thrombocytopenia (Lab) identified through grading of laboratory data per the NCI-CTCAE 4.03, by grade
- Hemorrhages as defined in [Section 2.1.4.1](#) by grade
- Hemorrhages following Grades 4 thrombocytopenia (Lab). The first hemorrhages event occurring within 8 days after any occurrence of the thrombocytopenia (Lab) will be used for this analysis.

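### The neutropenic-infection rule has no category for infections without a neutrophil count, and the matching hemorrhage rule misses bleeds that precede the platelet count and has two conflicting display conditions

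*SAP*

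**What the plan says.** **Neutropenic infection.** SAP 2.1.4.1 takes infections of Grade 2 or higher and pairs each with laboratory neutrophil values: "Infection and Grade 3-4 neutropenia will be considered as concomitant if one of the following condition is met". Three conditions are then listed. One is a value from the onset day itself. Another is that the latest earlier value "measured before the start date of the AE infection is within 7 days before the start of the AE infection". The remaining one uses the earliest later value, provided it is taken no more than 2 days after onset. No third category exists. SAP 2.5.3 on missing data is generic and gives no rule for an infection without a count.

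**When counts are taken.** Protocol 1.2, footnote m, schedules hematology weekly in the first cycle and twice per cycle (Days 1 and 15) in the next two. For Cycle 4 onward the wording is: "and then within 24 hours prior to study treatment administration on Day 1 of every subsequent cycle". Counts at end of treatment and when clinically indicated come on top.

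**What a Day 1 count can show.** Protocol 8.2.3.1: "A new cycle of study treatment may begin on the scheduled Day 1 of a subsequent cycle if the following criteria are met". One of those criteria is an ANC of at least 1000/mm3. Table 3 puts Grade 3 neutropenia below 1.0 x 10^9/L. If the criteria fail, patients are re-checked weekly.

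**Hemorrhage.** SAP 2.1.4.1 makes display conditional: "severe thrombocytopenia (ie, Grade 4) with concomitant hemorrhage will be displayed if relevant (ie, in case of imbalance between treatment arms". Its time window, repeated in 2.4.5.1, reads as follows: "The first hemorrhages event occurring within 8 days after any occurrence of the thrombocytopenia (Lab) will be used for this analysis". SAP 2.4.5.1 lists hemorrhages following Grade 4 thrombocytopenia among the tables to be provided and sets no condition.

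**The concern.** The definition treats an infection nobody tested as one that tested negative. That matters most where counts are sparse, which by design is late in treatment.

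The outcome carries weight in this trial. Protocol 4.5.3 rests part of its benefit/risk case on there being no increase in febrile neutropenia or neutropenic infection, despite 85.7% Grade 3-4 laboratory neutropenia in the Phase 1b study. SAP Table 1 records that neutropenic complications were added in version 2 to characterize safety better and to account for FDA comments.

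The hemorrhage rule looks forward only, so a bleed that leads to the first Grade 4 platelet count is not counted as concomitant with it. Making display depend on an observed imbalance is reporting a harm according to its result.

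**Working it through.** The plan states no coverage figure to reproduce, so the check enumerates onset days.

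**Inputs.** 28-day cycle and count days (Protocol 1.2, footnotes c and m). Window from 7 days before to 2 days after onset (SAP 2.1.4.1). ANC of at least 1000/mm3 to start a cycle (Protocol 8.2.3.1).

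**Rule.** An infection starting on day *d* is matchable if some count day *c* satisfies *d* - 7 <= *c* <= *d* + 2. So a count on day *c* serves onset days *c* - 2 to *c* + 7. Day 29 is the planned Day 1 of the next cycle.

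**Step 1: any scheduled count in the window.**
- Cycle 1 (Days 1, 8, 15, 22, 29): 28/28.
- Cycles 2-3 (Days 1, 15, 29): Days 1-8, 13-22, 27-28 = 20/28 (71%).
- Cycle 4 onward (Days 1, 29): Days 1-8, 27-28 = 10/28 (36%).

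**Step 2: only counts that can be Grade 3-4.** The Day 1 count of a cycle that has started must be at least 1.0 x 10^9/L, so it cannot flag an infection. For Cycle 1 Day 1 this is an assumption, based on exclusion E 11 at screening.
- Cycle 1 (Days 8, 15, 22): Days 6-28 = 23/28 (82%).
- Cycles 2-3 (Day 15): Days 13-22 = 10/28 (36%), or 12/28 (43%) if the Day 29 count is Grade 3-4.
- Cycle 4 onward: 0/28 if the next cycle starts on time, or 2/28 (7%, Days 27-28) if the Day 29 count is Grade 3-4.

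**Step 3: delays.** A Grade 3-4 count on Day 29 postpones the cycle, and the 7-day look-back then reaches Days 27-36. With a one-week delay that is about 10 of 35 days (29%); Day 36 is the restart day. If a share *q* of later cycles is delayed one week, the matchable share is 10*q*/(28 + 7*q*): 1.0/28.7 = 3.5% at *q* = 10%, 2.5/29.75 = 8.4% at 25%, 5.0/31.5 = 15.9% at 50%. The documents give no value for *q*.

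**Step 4: unscheduled counts.** If an infection prompts a count on Days 0 to +2 with probability *u*, the matchable share from Cycle 4 runs from *u* to *u* + (1 - *u*) x 2/28: 0-7% at *u* = 0, 50-54% at 0.5, 80-81% at 0.8. The documents give no value for *u*.

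**Step 5: hemorrhage.** Suppose a bleed starts on day *d* and prompts a first Grade 4 platelet count on day *d* + 1. The bleed is not after the count, so it is left out, unless an earlier Grade 4 count lies within the 8 days before it. Under the neutropenia rule, an infection followed by a count one day later is included. Whether a same-day bleed counts as after is not stated.

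**The case against.** The strongest objection is that the rule is not confined to scheduled counts. Any measured value qualifies, including clinically indicated ones and weekly re-checks during a delay. The dose-adjustment tables (Protocol Tables 3-6) also have separate rows for neutropenic infection and for infection without neutropenia, so an investigator needs a count near onset to choose between them. This stands. It means the scheduled-count figures describe what the schedule guarantees, not what the data will contain.

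It is also fair that little is hidden altogether. Febrile neutropenia comes from AE terms, all infections appear in the TEAE tables, all hemorrhages are tabulated by grade, and safety analyses are descriptive. What is affected is the concomitant subset.

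A reader might infer that the rule favours IPd, because longer treatment means more time from Cycle 4 on. The documents do not support that. Assume treatment lasts to the PFS event with exponential medians of 4 and 6.67 months (Protocol 11.1), full follow-up and no unscheduled counts, and take the higher Step 2 values. Mean days in Cycle 1, Cycles 2-3 and Cycle 4 onward are then 25.9, 40.9 and 108.9 (Pd) and 26.7, 46.3 and 219.9 (IPd). Flaggable days are 23/28 x 25.9 + 12/28 x 40.9 + 2/28 x 108.9 = 46.6 for Pd, and 57.5 for IPd by the same formula. The flaggable share of treatment time is lower in IPd (19.6% against 26.5%). But SAP 2.4.5.1 describes no exposure adjustment for this table, and per patient IPd has more flaggable days, a ratio of 1.23 against an exposure ratio of 1.67. IPd patients also attend for infusion on Day 15 of every later cycle (Protocol 8.2.1), which gives that arm more occasions for a count.

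A reader might also infer that late Grade 4 platelet values must come mainly from unscheduled counts. That does not follow: Table 3 provides for Grade 4 thrombocytopenia on Day 1, when a count is scheduled.

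**Conclusion.** The point holds as a gap in definition and reporting.
- An infection with no count in the window is classed as not neutropenic. This follows from the definition; the SAP does not say it in words.
- From Cycle 4 the schedule alone leaves most onset days unable to yield a match. The actual loss depends on unscheduled testing and cycle delays, neither of which the documents quantify. Neither the size of the undercount nor its direction between arms can be stated.
- The hemorrhage analysis excludes bleeds that come before the count they prompt, by an amount the documents do not allow to be estimated.
- SAP 2.1.4.1 and 2.4.5.1 contradict each other on whether the hemorrhage analysis is always shown. This needs no assumption.

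No primary or key secondary test is affected. The change is worth making because the current output cannot show a reader how many infections were never evaluable.

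**What to change.** In SAP 2.1.4.1 and 2.4.5.1:
1. Report Grade 2 or higher infections in three classes (neutropenic, not neutropenic, no count in window), by arm and by Cycle 1, Cycles 2-3 and Cycle 4 onward.
2. Delete the imbalance condition in 2.1.4.1 so that it agrees with 2.4.5.1, and always provide the hemorrhage table.
3. Accept a bleed starting up to 2 days before the Grade 4 platelet count, matching the look-ahead already allowed for neutropenia, and state that same-day bleeds count.

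Any AE-based or investigator-reported version of neutropenic infection should be a separate supplementary row. Merging it into the laboratory definition would bring investigator labels into an open-label comparison, and Protocol 1.2, footnote m, has hematological abnormalities recorded as AEs only if serious or if they lead to treatment modification or discontinuation.

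The cost is SAP wording and a little programming on data already collected. The reported hemorrhage percentage may rise slightly. SAP Table 10 lists other significant adverse events again at the second interim and final OS analyses, so the change is still of use after the primary analysis.

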### **Thrombocytopenia and hemorrhages**

- Thrombocytopenia will be analyzed based on laboratory results
- Hemorrhages will be selected using the TEAEs from the CMQ ‘Haemorrhage terms (excl laboratory terms)’.
- Moreover, severe thrombocytopenia (ie, Grade 4) with concomitant hemorrhage will be displayed if relevant (ie, in case of imbalance between treatment arms). The first hemorrhages event occurring within 8 days after any occurrence of the thrombocytopenia (Lab) will be used for this analysis.

### **Hemolytic disorders**

Hemolytic disorders will be selected using the TEAEs from the CMQ ‘Haemolytic disorders Broad’.

Hemolytic disorders that occurred within 8 days after the blood cell transfusion (red blood cells or platelets) will be displayed.

### **Tumor lysis syndrome**

Tumor lysis syndrome will be identified using the TEAEs from the CMQ ‘Tumour lysis syndrome’.

### **Autoimmune disorders**

Autoimmune disorders will be selected using the TEAE from the CMQ ‘GLB\_HLGT Autoimmune disorders’.

### **Second primary malignancies**

Second primary malignancies will be selected using CMQ ‘Second primary malignancies’ and will be sub-categorized as ‘haematological’, ‘non-hematological skin tumors’, ‘non-hematological non-skin tumors’ and ‘other tumors’.

### **COVID19**

COVID19 related TEAEs will be selected using CMQ ‘COVID19\_specific list’.

#### 2.1.4.2 Deaths

The deaths observation periods are per the observation periods defined above.

- Death on-treatment: deaths occurring during the TEAE period.
- Death post-treatment: deaths occurring during the post-treatment period.

